Dr. [name] should be contacted directly at these numbers to report medical concerns or questions regarding safety.

[contact]

[contact], [name]

DISCONTINUATION AND REPLACEMENT OF SUBJECTS

Early Discontinuation of Study Drug (Lemborexant)

A subject may be discontinued from study treatment at any time if the subject or the investigator feels that it is not in the subject's best interest to continue. The following is a list of possible reasons for study treatment discontinuation:

Subject withdrawal of consent (or assent)

Subject is not compliant with study procedures

Adverse event that in the opinion of the investigator would be in the best interest of the subject to discontinue study treatment

Lost to follow-up

Sponsor request for early termination of study

Positive pregnancy test (females)

If a subject is withdrawn from treatment due to an adverse event, the subject will be followed and treated by the Investigator until the abnormal parameter or symptom has resolved or stabilized.

All subjects who discontinue study treatment should come in for an early discontinuation visit as soon as possible and then should be encouraged to complete all remaining scheduled visits and procedures.

All subjects are free to withdraw from participation at any time, for any reason, specified or unspecified, and without prejudice.

Reasonable attempts will be made by the investigator to provide a reason for subject withdrawals. The reason for the subject's withdrawal from the study will be specified in the subject's source documents.

Withdrawal of Subjects from the Study

A subject may be withdrawn from the study at any time if the subject, the investigator, or the Sponsor feels that it is not in the subject's best interest to continue.

All subjects are free to withdraw from participation at any time, for any reason, specified or unspecified, and without prejudice.

Reasonable attempts will be made by the investigator to provide a reason for subject withdrawals. The reason for the subject's withdrawal from the study will be specified in the subject's source documents.

Replacement of Subjects

Subjects who withdraw from the study treatment will be replaced.

Subjects who withdraw from the study will be replaced.

Protocol Violations

A protocol violation occurs when the investigator fails to adhere to significant protocol requirements affecting the inclusion, exclusion, subject safety and primary endpoint criteria except when performed for participant safety. Protocol violations for this study include, but are not limited to, the following:

Failure to meet inclusion/exclusion criteria

Failure to comply with Good Clinical Practice (GCP) guidelines will also result in a protocol violation. The investigator will determine if a protocol violation will result in withdrawal of a subject.

When a protocol violation occurs, it will be discussed with the investigator and a Protocol Violation Form detailing the violation will be generated. A copy of the form will be filed in the site's regulatory binder, and these will be reported to VCU IRB and the DSMB.

DATA SAFETY MONITORING

The Data Safety and Monitoring Plan includes establishment of a Data Safety Monitoring Board who will include five individuals who are completely independent of the investigators and who have no financial, scientific, or other conflict of interest with the trial. Each member will provide written documentation attesting to absence of conflict of interest. Additionally, [name] will serve as the on site medical monitor for the study.

For full data safety monitoring information see the Data Safety Monitoring Plan.

STATISTICAL METHODS AND CONSIDERATIONS

Initial analyses will evaluate group differences on demographic and baseline variables, will use contingency tables with chi-square testing, ANOVA's, and examination of correlations between baseline variables subjective responses and clinical results. General data analysis procedures: Prior to data analysis procedures, groups will be examined for differences in baseline characteristics that could potentially influence treatment outcome. Any variables that differ between groups and are related to outcome measures will be examined as potential covariates in subsequent data analyses.

Primary outcome measures:

1. Safety: Heart rate (HR), blood pressure (BP), respiratory rate, agitation and sedation (Richmond Agitation-Sedation Scale) and pulse oximetry during a placebo dose will be compared to HR and BP after each lemborexant dose (5 mg and 10 mg doses). Changes in safety measures induced by lemborexant dose along with buprenorphine will be compared to those without lemborexant, by lemborexant dose level (5 mg and 10

mg doses), using a generalized linear mixed model analysis with the participant as a random effect for each outcome. Adverse event data will be compiled for lemborexant and placebo cohorts and presented as summary statistics.

2. Buprenorphine PK: Plasma concentration-time profiles of buprenorphine and its metabolite norbuprenorphine after doses during the lemborexant placebo/administration (Day 0, 1, 2) will be analyzed to obtain pharmacokinetic parameter estimates of buprenorphine (Cmax, Tmax, AUC, apparent t_{1/2}, CL/F for parent buprenorphine and metabolic (AUC) ratios for metabolites) by individual. These parameters will be compared within subjects on sessions with lemborexant. Lemborexant PK will be compared with published lemborexant PK data. As it would be unethical to withhold buprenorphine treatment from patients who are on buprenorphine for MAT, there will be no lemborexant dose without buprenorphine.

3. Changes in secondary outcome measures induced by lemborexant dose along with buprenorphine will be compared to those without lemborexant, by lemborexant dose level (5 mg and 10 mg doses), using a generalized linear mixed model analysis with the participant as a random effect for each outcome.

Safety and tolerability data will be summarized by treatment group.

Adverse event rates will be coded by body system and MedDra classification term. Adverse events will be tabulated by treatment group and will include the number of patients for whom the event occurred, the rate of occurrence, and the severity and relationship to study drug.

Interim Analysis

There will be no formal interim analysis.

Rationale for sample size: Sample size for effect of lemborexant on recommendations from the FDA regarding phase I safety studies.

DATA COLLECTION, RETENTION AND MONITORING

Data Collection Instruments

The Investigator will prepare and maintain adequate and accurate source documents designed to record all observations and other pertinent data for each subject treated with the study drug.

Study personnel at each site will enter data from source documents corresponding to a subject's visit into the protocol-specific paper/electronic CRF when the information corresponding to that visit is available. Subjects will not be identified by name in the study database or on any study documents to be collected by the Sponsor (or designee), but will be identified by a subject number.

The Investigator is responsible for all information collected on subjects enrolled in this study. All data collected during the course of this study must be reviewed and verified for completeness and accuracy by the Investigator.

Data Management Procedures

The data will be entered into a REDCap database and OnCore. The Data Management group will be responsible for data processing, in accordance with procedural documentation. Database lock will occur once quality assurance procedures have been completed. All procedures for the handling and analysis of data will be conducted using good computing practices meeting FDA guidelines for the handling and analysis of data for clinical trials.

Data Quality Control and Reporting

After data have been entered into the study database, a system of computerized data validation checks will be implemented and applied to the database on a regular basis. The study database will be updated in accordance with the resolved queries. All changes to the study database will be documented.

Archival of Data

The database is safeguarded against unauthorized access by established security procedures; appropriate backup copies of the database and related software files will be maintained. Databases are backed up by the database administrator in conjunction with any updates or changes to the database. At critical junctures of the protocol (e.g., production of interim reports and final reports), data for analysis is locked and cleaned per established procedures.

Availability and Retention of Investigational Records

The Investigator will make study data accessible to IRB, and Regulatory Agency (e.g., FDA) inspectors upon request. A file for each subject must be maintained that includes the signed Informed Consent, HIPAA Authorization and Assent Form and copies of all source documentation related to that subject. The Investigator will ensure the reliability and availability of source documents from which the information on the CRF was derived. All study documents (patient files, signed informed consent forms, copies of CRFs, Study File Notebook, etc.) will be kept secured for a period of six years after study completion and the IND has been discontinued.

Subject Confidentiality

In order to maintain subject confidentiality, only a subject number will identify all study subjects on CRFs and other documentation submitted to the Sponsor. In addition, a Certificate of Confidentiality will be issued by NIDA to protect subject confidentiality.

ADMINISTRATIVE, ETHICAL, REGULATORY CONSIDERATIONS

The study will be conducted according to the Declaration of Helsinki, Protection of Human Volunteers (21 CFR 50), Institutional Review Boards (21 CFR 56), and Obligations of Clinical Investigators (21 CFR 312).

To maintain confidentiality, all laboratory specimens, evaluation forms, reports and other records will be identified by a coded number and initials only. All study records will be kept in a locked file cabinet and code sheets linking a patient's name to a patient identification number will be stored separately in another locked file cabinet. Clinical information will not be released without written permission of the subject, except as necessary for monitoring by the FDA. The Investigator must also comply with all applicable privacy regulations (e.g., Health Insurance Portability and Accountability Act of 1996, EU Data Protection Directive 95/46/EC).

Protocol Amendments

Any amendment to the protocol will be written by the investigator. Protocol amendments cannot be implemented without prior written IRB approval except as necessary to eliminate immediate safety hazards to patients. A protocol amendment intended to eliminate an apparent immediate hazard to patients may be implemented immediately, provided the IRB is notified subsequently.

Institutional Review Boards and Independent Ethics Committees

The protocol and consent form will be reviewed and approved by the VCU IRB or Western IRB prior to study initiation. Serious adverse experiences regardless of causality will be reported to the IRB in accordance with

the standard operating procedures and policies of the IRB, and the Investigator will keep the IRB informed as to the progress of the study. The Investigator will obtain assurance of IRB compliance with regulations.

Any documents that the IRB may need to fulfill its responsibilities (such as protocol, protocol amendments, Investigator's Brochure, consent forms, information concerning patient recruitment, payment or compensation procedures, or other pertinent information) will be submitted to the IRB. The IRBs written unconditional approval of the study protocol and the informed consent form will be in the possession of the Investigator before the study is initiated.

Protocol and/or informed consent modifications or changes may not be initiated without prior written IRB approval except when necessary to eliminate immediate hazards to the patients or when the change(s) involves only logistical or administrative aspects of the study. Such modifications will be submitted to the IRB and written verification that the modification was submitted and subsequently approved should be obtained.

[figure not shown]
The IRB must be informed of revisions to other documents originally submitted for review; serious and/or unexpected adverse experiences occurring during the study in accordance with the standard operating procedures and policies of the IRB; new information that may affect adversely the safety of the patients of the conduct of the study; an annual update and/or request for re-approval; and when the study has been completed.

Informed Consent Form

[figure not shown]
Informed consent will be obtained in accordance with the Declaration of Helsinki, ICH GCP, US Code of Federal Regulations for Protection of Human Subjects (21 CFR 50.25[a,b], CFR 50.27, and CFR Part 56, Subpart A), the Health Insurance Portability and Accountability Act (HIPAA, if applicable), and local regulations. The Investigator will prepare the informed consent form and HIPAA authorization. The written consent document will embody the elements of informed consent as described in the International Conference on Harmonization and will also comply with local regulations. A properly executed, written, informed consent will be obtained from each subject prior to entering the subject into the trial. Information should be given in both oral and written form and subjects must be given ample opportunity to inquire about details of the study. A copy of the signed consent form will be given to the subject and the original will be maintained with the subject's records.

Publications

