| STATISTICS Primary Analysis Plan | 
Initial analyses will evaluate group differences on demographic and baseline variables, will use contingency tables with chi-square testing, ANOVA's, and examination of correlations between baseline variables, subjective responses, and clinical results. General data analysis procedures: Prior to data analysis procedures, groups will be examined for differences in baseline characteristics that could potentially influence treatment outcome. Any variables that differ between groups and are related to outcome measures will be examined as potential covariates in subsequent data analyses.
 
Primary outcome measures:
 
 1. Safety: Heart rate (HR), blood pressure (BP), respiratory rate, agitation and sedation (Richmond Agitation-Sedation Scale) and pulse oximetry during a placebo dose will be compared to HR and BP during each lemborexant dose (5 mg and 10mg doses). Changes in safety measures induced by lemborexant dose along with buprenorphine will be compared to those without lemborexant, by lemborexant dose level (5 mg and 10 mg doses), using a generalized linear mixed model analysis with the participant as a random effect for each outcome. Adverse event data will be compiled for lemborexant and placebo cohorts and presented as summary statistics. 2. Buprenorphine PK: Plasma concentration-time profiles of buprenorphine and its metabolite norbuprenorphine after doses during the lemborexant placebo/administration (Day 0,1, 2) will be analyzed to obtain pharmacokinetic parameter estimates of buprenorphine (Cmax, Tmax, AUC, apparent t½, CL/F for parent buprenorphine and metabolic (AUC) ratios for metabolites) by individual. These parameters will be compared within subjects on sessions with lemborexant. 3. Changes in secondary outcome and exploratory outcome measures induced by lemborexant dose along with buprenorphine will be compared to those without lemborexant, by lemborexant dose level (5 mg and 10 mg doses), using a generalized linear mixed model analysis with the participant as a random effect for each outcome. |

| | |
|----------------------------------|---|
| RATIONALE FOR NUMBER OF SUBJECTS | Projected sample size is 18 subjects who have completed at least one drug-drug interaction treatment session with primary endpoint data— 12 lemborexant-treated subjects, 6 placebo treated subjects. Sample size was determined based on primary outcome safety and PK measures. |

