The primary risks occur during administration of lemborexant with buprenorphine-naloxone. This will take place on the clinical research unit, under supervision of providers and trained nursing staff who will immediately respond to any adverse event. Participants will spend the night on the CRU prior to lemborexant administration to ensure that they do not take any additional drugs or medications that could interact with lemborexant.

The identification of effective treatments for opioid use disorder would be a great benefit to society.

If any Psychiatric or non-Psychiatric medical illness (other than substance abuse) is discovered during the study, subjects will be referred for additional treatment in the community.

STUDY DESIGN

Overview

We propose a series of experiments to study the safety and target engagement of lemborexant when combined with buprenorphine-naloxone for opioid use disorder.

Study Design: Pharmacokinetic safety and pharmacodynamic efficacy signal trial of combined lemborexant and buprenorphine-naloxone (see Figure 1 below).

STUDY OVERVIEW/SCHEMA

[figure not shown]

Figure 1. Overall Study Design

Participants will include 18 individuals (goal of 9 male and 9 female) with opioid use disorder in medication assisted treatment who are a buprenorphine-naloxone sublingual film daily dose ranging from 8mg/2mg to 24mg/6mg or buprenorphine sublingual tablet dose ranging from 5.7mg/1.4mg to 17.1/4.3 once daily at the VCU MOTIVATE or other outpatient treatment setting who complete at least one drug-drug interaction treatment session with primary endpoint data (at least 12 lemborexant treated participants and 6 placebo treated subjects).

After a complete screening including the phenotyping assessment battery (PhAB) described in detail below,

participants will be randomized to either lemborexant (12 participants) or placebo (6 participants) and will undergo safety and PK testing on the CRSU at VCU, as described in Tables 1 and 2 below. We will characterize the pharmacokinetic (PK) and pharmacodynamic (PD) profiles of the combined administration of lemborexant with buprenorphine-naloxone including the time to onset, duration of action, magnitude of effects, and the pharmacokinetic disposition of buprenorphine and its major metabolite in plasma.

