If subjects meet inclusion criteria, they will be admitted as research participants to the clinical research unit (CRU) for a total of up to 4 overnight stays across the two inpatient admission visits to maintain complete monitoring for adverse events. While in the hospital, subjects will undergo procedures as described below. Subjects will not be allowed to smoke cigarettes, as smoking is not allowed in the hospital or anywhere on the VCU campus. Subjects who are identified as current smokers will have the option to use a nicotine patch dosed based on the amount of daily cigarettes smoked. Subjects will not be allowed to leave the CRU nor receive visitors if they wish to remain in the study. Subjects who are unable to comply with these restrictions will be dropped from the study. Eligible subjects will be randomized to Group A –placebo only or Group B – lemborexant. Six subjects will be assigned to Group A (placebo) and 12 subjects will be assigned to Group B (active lemborexant).

Study Drug Dosage: 5 mg of lemborexant, and 10 mg of lemborexant, all subjects will receive a dose equivalent to their current prescribed dose of buprenorphine-naloxone sublingually as a film or tablet.

STUDY OUTCOME MEAURES

Primary outcome measures:

1. Safety: Heart rate (HR), blood pressure (BP), respiratory rate, agitation and sedation (Richmond Agitation-Sedation Scale), capnography (EtCO₂), and pulse oximetry during placebo administration will be compared to those same measures after lemborexant. Changes in safety measures induced by buprenorphine-naloxone dose along with lemborexant will be compared to those without lemborexant. Adverse event data will be compiled for lemborexant and placebo cohorts and presented as summary statistics.
2. Buprenorphine PK: Plasma concentration-time profiles of buprenorphine and its metabolite norbuprenorphine and after doses during the lemborexant placebo/administration (Day 0,1, 2) will be analyzed to obtain pharmacokinetic parameter estimates of buprenorphine (C_{max}, T_{max}, AUC, apparent t_{1/2}, CL/F for parent buprenorphine and metabolic (AUC) ratios for metabolites) by individual. In addition lemborexant and its main metabolite M10 will be determined after each dose of buprenorphine and compared with published lemborexant PK parameters.

Secondary Outcome Measures:

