1. Subjective effects on opioid craving and anxiety as measured by a visual analog scale, and brief substance craving scale, and opioid withdrawal based on the Subjective Opioid Withdrawal Scale.
2. Objective opioid withdrawal based on the Clinical Opioid Withdrawal Scale.
3. Impulsivity as measured by delayed discounting. All measures will be compared between subjects receiving lemborexant versus those on placebo to determine the extent to which this measure is modified by the administration of lemborexant with buprenorphine vs. placebo with buprenorphine.

Exploratory Outcome Measures:

1. Pupillometry is used to measure change in pupil size as an indicator of lemborexant changes in buprenorphine central nervous system mu-opioid pharmacological effects (Rollins, Feiner et al. 2014). Single pupil measurements at scheduled times will be performed using a pupillometer per manufacturer's specification. The light in the measurement room will be maintained at 3.6 to 4.3 lux, using a Lutron light meter. Participants will be allowed to adjust to the room lighting for at least 3 minutes prior to any measurement. Pupillometry will be measured using the right eye for all participants, unless otherwise determined by the Investigator. The same eye will be used for all measurements in the study.
2. Sleep quality as measured by sleep diary and Pittsburgh Sleep Quality Index.
3. Relationship between baseline behavioral profiles as determined by the NIDA Phenotyping Battery and subjective response to lemborexant.

STUDY DRUG AND DOSAGE

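### Baseline adjustment of the lemborexant–placebo contrasts rests on a data-driven screen in about 12 v 6 people; no model names a baseline value or says where the compared changes start

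*Combined protocol and SAP*

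**What the plan says.** All references are to the combined protocol and SAP.

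- **Covariates.** Statistical Methods and Considerations, and in the same words the Statistics row of the synopsis: "Any variables that differ between groups and are related to outcome measures will be examined as potential covariates in subsequent data analyses". Differences and relations are to be sought with chi-square tests, ANOVAs and correlations on the trial's own data. No significance level and no covariate list is given.
- **Contrast.** Study Outcome Measures says of safety that "pulse oximetry during placebo administration will be compared to those same measures after lemborexant", and of the secondary outcomes that "All measures will be compared between subjects receiving lemborexant versus those on placebo". Placebo is a separate randomised arm (12 v 6, Study Design overview), so the contrast is between people.
- **Models.** For safety: "Changes in safety measures induced by lemborexant dose along with buprenorphine will be compared to those without lemborexant", by dose level, "using a generalized linear mixed model analysis with the participant as a random effect for each outcome". For secondary outcomes: "Changes in secondary outcome measures induced by lemborexant dose along with buprenorphine will be compared to those without lemborexant", with the same model. Pupil size is covered only by item 3 of the synopsis: "Changes in secondary outcome and exploratory outcome measures induced by lemborexant dose along with buprenorphine will be compared to those without lemborexant". The matching item in the body leaves exploratory outcomes out. The statistical text names Day 0 only for buprenorphine PK.
- **Data available.** Table 2 schedules vital signs, oximetry and capnography, RASS, craving and withdrawal scales, VAS, delay discounting and pupil size on Day 0, when buprenorphine-naloxone is given without study drug. The same measures are taken on Day 2 of each testing week.

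**The concern.** A test of baseline difference in 12 v 6 people has little power, so a screen built on it will rarely bring in even a strongly prognostic baseline. Whether it does depends on the observed data and on a threshold that nobody has set.

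The unstated starting point of the changes makes this worse. The participant random effect does not settle how Day 0 enters:

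- Day 0 as a repeated response with a mean common to both arms: the contrast is already adjusted.
- Day 0 as a repeated response with arm-specific means: the contrast is the change score.
- Day 0 left out: the contrast is the raw post-dose value.

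Under a chance imbalance, raw values and change scores err in opposite directions, so this choice can alter a result. At stake are the precision of an 18-completer trial, on outcomes that include primary safety measures, and a final model that is fixed only after the data are seen.

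**Working it through.** **Inputs.** From the documents: 18 completers, allocated 2:1, hence 12 and 6. The plan gives no power, alpha, SD or effect size, so apart from that split there is no figure of its own to reproduce. Assumed: SD = 1, screening alpha 0.05 (0.10 and 0.20 also shown), and correlation r between Day 0 and the post-dose value of 0.3 to 0.8.

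**1. What the screen can see.** The standard error of a baseline difference is √(1/12 + 1/6) = 0.50 SD. On 16 df, the smallest difference flagged at alpha 0.05/0.10/0.20 is 2.12/1.75/1.34 × 0.50 = 1.06/0.87/0.67 SD.

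**2. Variance relative to raw values.** ANCOVA on Day 0: (1 − r²) × (1 + 1/14), where 1/14 is the small-sample price of estimating the slope with 16 within-arm df. Change from Day 0: 2(1 − r). Example at r = 0.5: 0.75 × 15/14 = 0.80, and 2 × 0.5 = 1.00.

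**3. Simulation** (12 v 6, normal Day 0 and one post-dose value, no true effect, 200,000 trials per r). The screen opens when both the baseline difference and the correlation with outcome have p < alpha. The simulated variance ratios agree with step 2.

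| | r = 0.3 | 0.5 | 0.6 | 0.8 |
|---|---|---|---|---|
| ANCOVA / raw | 0.98 | 0.80 | 0.69 | 0.39 |
| ANCOVA / change from Day 0 | 0.70 | 0.80 | 0.86 | 0.96 |
| Screen opens, alpha 0.05 | 1.2% | 2.9% | 4.0% | 4.9% |
| Screen opens, alpha 0.20 | 9.8% | 16.5% | 18.6% | 20.0% |
| ANCOVA / screen on raw, alpha 0.05 | 0.99 | 0.84 | 0.74 | 0.46 |
| ANCOVA / screen on raw, alpha 0.20 | 1.02 | 0.92 | 0.85 | 0.63 |
| ANCOVA / screen on change, alpha 0.05 | 0.70 | 0.81 | 0.87 | 0.97 |
| ANCOVA / screen on change, alpha 0.20 | 0.73 | 0.86 | 0.92 | 0.98 |

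From 0.50 SD for raw values, the standard error under ANCOVA falls to 0.45/0.41/0.31 SD at r = 0.5/0.6/0.8.

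**4. Missed imbalances.** At alpha 0.05, 27% of trials have a non-significant Day 0 imbalance above 0.5 SD, with mean size 0.70 SD. Aligned with the sign of the imbalance, the error is r × 0.70 for raw values and (r − 1) × 0.70 for change scores. At r = 0.5/0.6/0.8 that is +0.35/+0.42/+0.56 SD and −0.35/−0.28/−0.14 SD. It is about 0 for ANCOVA. Averaged without regard to sign, the error is about 0 for all three.

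**5. Type I error.** Under the screen it is about 2% to 5% across these settings; under ANCOVA it is 5.0%.

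**6. Day 0 as a repeated response.** With Day 0 and two dosing sessions (equal correlations, second-session contrast), a common Day 0 mean gives 0.77/0.66/0.37 of the raw variance at r = 0.5/0.6/0.8. The Day 0 covariate gives 0.79/0.67/0.38, so it adds nothing there. Arm-specific Day 0 means reproduce the change-score variance exactly.

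**The case against.** - **Changes may be measured within a session.** A change induced by a dose can naturally mean pre-dose to post-dose on the same morning. Such a change has 2(1 − r) = 0.8/0.6/0.4 of the raw variance if pre-dose and post-dose values correlate at 0.6/0.7/0.8. Day 0 ANCOVA at r = 0.5 has 0.80, which is 1.0/1.3/2.0 times as much. This stands: forcing Day 0 could lose precision.
- **A closer baseline may exist.** A reader might infer from Table 2 that no pre-dose reading is taken on Day 2. The table marks days and not clock times, so it does not show that. Vital signs and the craving and withdrawal scales are also taken on Day 1. This stands.
- **The mixed model may already adjust.** The sessions without lemborexant could include Day 0, and with a common Day 0 mean the gain from the fix is nil. This stands as a possible reading, but nothing in the text selects it.
- **Other covariates are not barred.** The sentence does not exclude them. True, but no other covariate rule is stated.
- **The gain may be small.** Table 1 makes Day 0 an outpatient visit, while dosing follows an overnight stay without smoking, so r may be low. Testing weeks may also be about 14 days apart, which may lower r in week 2. RASS, and possibly COWS, SOWS and SpO2, may sit at floor or ceiling in stable patients; these were not quantified. This limits the size of the point but does not justify a test-based screen.

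**Conclusion.** The point holds as a matter of precision and prespecification. The only stated covariate rule would almost never adjust these between-arm contrasts at alpha 0.05. No model names a baseline, and the start of the changes is unstated although suitable data are collected.

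The size depends on assumed correlations, normal data, and 12 and 6 people analysed. Against raw values, Day 0 adjustment cuts variance by 20/31/61% at r = 0.5/0.6/0.8 and by about 2% at r = 0.3. Against change from Day 0 it cuts 20/14/4% at r = 0.5/0.6/0.8. It gains nothing if Day 0 is already a repeated response with a common mean.

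A reader might infer that the screen biases the trial or inflates false positives. It does neither on average: the mean error is about 0 and type I error does not exceed about 5%. A reader might also infer that Day 0 must be the sole reference for change. The documents do not support that, because a reading closer to dosing but before the first study-drug dose may exist and may serve better. The change is worth making before unblinding, with moderate confidence about how much it gains.

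**What to change.** Replace the screening sentence in the synopsis and in Statistical Methods and Considerations with:

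> Baseline characteristics will be described by arm; no covariate will be selected by a test of baseline difference or by its observed relation to outcome. Each between-arm mixed model for a safety, secondary or pupil outcome will include the participant's pre-study-drug baseline value of that outcome as a prespecified covariate, or that baseline as a repeated response with a common mean across arms, but not both.

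The baseline is the Day 0 value by default. Where a reading before the first study-drug dose is taken closer to dosing (Week 1 Day 1, or Week 1 Day 2 pre-dose), the SAP may name it instead of Day 0 or in addition. Week 2 pre-dose values should not serve as the baseline covariate, because they follow the first study-drug dose.

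Before unblinding, the SAP should name for each outcome the baseline and its time window, the model form, and any other prespecified covariates. The window needs thought for serial measures: Table 3 puts lemborexant at 7:05 and buprenorphine at 8:05, so the first hour after lemborexant has no Day 0 counterpart. Leave out PK, and the VAS items on drug liking, drug disliking and good or bad drug effect.

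The cost is SAP wording, one decision on the window for each serial outcome, and about one degree of freedom per model. No visit or measurement is added. At r = 0.3 the result ranges from 1% better to 2% worse than the screen applied to raw values.
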